Aim #4: To compare the overall cost. There are several differences between the two surgical reconstruction methods as outlined in the background. The differences have implications for reducing several factors associated with operative time. The average decrease in operation time for orbital reconstruction with selective laser-melting patient-specific implants is 0.40–3.82 hours.⁽¹⁷⁾

- **Hypothesis #4:** The total overall operative cost will be significantly **lower** than for non-patient-specific orbital implants.

BACKGROUND

Facial trauma is among the most common traumas seen in urban trauma centers,⁽¹⁾ and orbital fractures are common in blunt facial trauma. The 3 patterns of orbital fractures are linear, complex, and isolated orbital floor fractures. Linear orbital fractures do not result in a defect. Complex orbital fractures involve extensive facial fractures that affect 2 or more orbital walls and are usually associated with Le Fort II and Le Fort III fractures. Isolated orbital floor fractures affect only one wall, with less than a 2-cm-diameter defect.⁽¹⁸⁾ The incidence of orbital fractures among all facial fractures is approximately 49%; this rate changes depending on the study. Complex orbital fractures represent 66% of all orbital fractures,⁽¹⁹⁾ and 22%–47% are isolated orbital floor fractures.^(3, 12)

Over the past two years, GMH has cared for 90 isolated orbital floor fractures. With respect to the **total orbital fractures (complex and isolated types), these numbers increased to 126 cases over the years 2016 and 2017.** Indications for surgery include retrobulbar hematoma, inferior rectus muscle entrapment, enophthalmos larger than 2 mm during the first 6 weeks, fracture involving more than 50% of the orbital floor, and diplopia in the primary field of gaze that fails to resolve after 2 weeks.^(3, 7) Titanium mesh is the current recommended material due to its availability, biocompatibility, cost-effectiveness, and low susceptibility to infection.^(12, 20)

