- Extra-ocular motility as assessed through clinical examination. The patient should be able to move the eyes through the six cardinal positions of gaze (left, right, up and right, up and left, down and right, down and left). All patients will be examined for the following:
 1. Development of restricted extraocular motility that was not present prior to the surgery.

2. Persistent restriction of extraocular motility after the surgery.

- Plate contour
 - Inability to achieve the normal orbital contour as assessed in the immediate post-operative CT scan.
- Operating time
 - This will be calculated from fracture exposure and identification to the final implant placement and fixation and will be recorded in minutes.
- Length of stay
 - 1- Isolated orbital floor fracture patients do not require a pre-operative hospital stay. Length of stay will be calculated in terms of post-operative hospital stay (days).
 - 2- Length of stay in cases of complex orbital fracture will be calculated in terms of pre-operative and post-operative hospital stay (days).
- Treatment charges

This will be calculated with consideration of the following:

- 1- Facility operating room charges, which include anesthesia time (surgical time multiplied by the facility rate of \$33/ minute).
- 2- Hardware charges (plates and screws).
- 3- LOS charges (LOS multiplied by the facility daily rate of \$1,690/ day).
- 4- The cost of the 3D printed model including the cost of the 3D printer and filaments (\$1.5).

All treatment charges variables will be provided by the GMH Financial Planning and Analysis center. Total treatment charges facility operating room charges, hardware charges, LOS, and the 3D printed model cost will be compared between groups in a manner similar to that outlined by Bouloux et al. ⁽²⁴⁾

Randomization Sample Size & Calculation

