We expect a **sample size of 60** surgical cases, evenly split between the new treatment and control groups, to have a study powered to **detect at least a 1 cm³ difference in orbital volume** between the groups. The sample size calculation was based on using a two-sample Student's t-test to compare the difference in contralateral orbital volume between the treatment and control groups. We used a **power of 90%**, alpha level of .05, and 1.17 cm³ standard deviation of orbital volume. The 'normal' orbital volume and standard deviation were estimated from the results of Forbes et al. (1984). Sample size calculations were performed with the 'power.t.test' function in R statistical software based on Cohen (1988).⁽²⁵⁾ Taking attrition into account, if 25% of our expected patient enrollment numbers are not met for any reason, **our study would still retain a power of 80%**. Additionally, in the event of attrition from loss-to-follow-up alone, our primary outcomes variable and the bulk of the secondary outcomes variables, including the reduction of orbital volume to less than 2 cm³, operative time, traumatic pupillary mydriasis, orbital compartment syndrome, extra-ocular motility, and plate contour, will be successfully obtained on immediate post-operative hour. **Attrition at these stages will have no effect on the above variables.**

Randomization & Statistical Analysis

Cases will be randomized to the treatment or control arms using a pre-generated block randomization scheme with a **block size of 4** and stratified according to surgeon/specialty. In essence, each surgeon will receive their own list of randomized cases to simplify the logistics of the trial. **The block randomization guarantees that at no point during the trial will there be more than a 3-case difference between the treatment and control arms for each individual surgeon**; thus, it is possible but unlikely that there will be a maximum 9 case difference at some

point (sizes will be equal at completion). The randomization scheme has been pre-generated by a statistician, and the resulting trial arm for each case will be placed in envelopes to be revealed at the time of patient enrollment. The treatment will not be blinded to the physician or the patient; it is not practical to keep knowledge of the procedure concealed.

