The success of the randomization will be evaluated at the start of the analysis by comparing patient characteristics. Differences between the treatment and control arms that do not reach statistical significance using appropriate tests (likely t-tests and chi-square tests) that are smaller than 20% for all characteristics will mean that the groups are ‘balanced’ in our criteria and will be evidence of randomization success. Assuming that standardization is successful, all outcomes will be compared using standard two-sample comparisons. For binary outcomes, such as complications and CT use, Chi-square tests or Fisher’s exact tests will be used depending on the prevalence of the outcome. Two-sample t-tests or Wilcoxon-Mann-Whitney tests (if data are non-parametric) will be used to compare mean orbital volume differences and operative times. Differences in length of stay and costs are likely to be analyzed with two sample t-tests on a log scale (thus, a comparison of geometric means will be made). Finally, logistic regression or other multivariable analyses may be performed to identify risk factors for developing complications or deviations from the normal recovery course.

Statistical Support

Support for statistical analyses will be provided by [name], MSPH, a trained biostatistician, working for the Department of Surgery at Emory University Hospital. All analyses will be conducted or supervised by [name]. [name] has 15 years of experience in data analysis and 7 years of experience working as the department statistician for surgery. He has over 40 peer-reviewed publications to his name and experience with outcomes and health services research as well as basic science research. In the past, he has assisted in the design and analysis of similar trials at Emory University. Regarding the cost-effective analysis, [name] is the primary mentor. He is an experienced researcher and participated in cost-effective research in GMH by comparing the cost effectiveness of 2 types of mandibular fracture treatment. ⁽²⁴⁾

Inclusion & Exclusion Criteria

- The following subjects will be included in the study:
 - 1- Agreed to be enrolled in the study.
 - 2- Indications for surgical repair of orbital floor and/ wall fractures are dependent on several factors:
 - a. Correction or prevention of cosmetic deformity (enophthalmos or inferior dystopia; disruption of greater than 50% of the orbital floor is likely to cause cosmetically apparent enophthalmos.

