- Complex orbital fractures will be exposed and identified via a transconjunctival approach in combination with lateral cantholysis if needed to improve access.
- To record and compare the operative time between the two groups, a stopwatch will be utilized. The time in minutes will be recorded from fracture exposure and identification to final implant placement and fixation.

Postoperative Assessment

During post-operative care, all patients will undergo the following:

- 1) Maxillofacial non-contrast CT scans according to the protocol will be obtained as part of the standard of care in managing orbital fractures.
- 2) The PI will evaluate the orbital volume using OsiriX (medical software). Orbital volume measurements will be obtained to compare the injured and uninjured (contralateral) orbital volumes. OsiriX MD offers advanced processing techniques and has the ability to precisely measure orbital volume. It utilizes the DICOM data from the immediate post-operative CT scans.
- 3) All patients, regardless of the group into which they are randomized, will receive their post-operative assessment by the designated team resident under the supervision of one of the following attendings: [name] for OMFS, [name] for ENT, or [name] for Plastic Surgery.
- 4) All patients, regardless of the group into which they are randomized, will receive their post-operative ocular assessment by [name], ophthalmology attending and Co-PI, or by her fellow [name].

Follow-Up

- All patients will be regularly assessed at 1 week, 3 weeks, and 6 weeks postoperatively.

This is a standard post-operative follow-up schedule for craniomaxillofacial fracture patients. It is also an adequate duration for edema to resolve, which will assist in the accurate evaluation of enophthalmos. The following will be evaluated and recorded by the surgical team at each follow-up visit: enophthalmos, infection, infraorbital nerve injury, traumatic pupillary mydriasis, orbital compartment syndrome, and restricted extra-ocular movement.

- In terms of data collection and data extraction from Epic: PI [name], co-PI [name] and an assigned research coordinator will be involved.

Patient Compensation

All patients enrolled in the study will be compensated with \$100 for their time and to encourage compliance. Their compensation includes the costs of participation in the study (\$50) and the completion of the follow-up visits at week 6.

Data Collection & Analysis

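### Operating time, length of stay and charges are compared without adjusting for fracture type, although isolated and complex fractures are both enrolled and the type is recorded before surgery

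*Combined protocol and SAP*

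**What the plan says.** **Who is enrolled.** The surgical approach under Intra-operative Assessment and the length-of-stay rule under Methodology both provide for isolated and for complex fractures. The Background says "Complex orbital fractures involve extensive facial fractures that affect 2 or more orbital walls" and links them with Le Fort II and III fractures. Inclusion criterion 4 asks for a unilateral orbital floor fracture and does not exclude other facial fractures.

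**What is measured.** One stopwatch rule serves every case: "The time in minutes will be recorded from fracture exposure and identification to final implant placement and fixation". Treatment charges have four parts:
- operating-room charges at $33 per minute of surgical time, a term that is not defined;
- "Hardware charges (plates and screws"), with no statement of which plates and screws count;
- length of stay at $1,690 per day, where pre-operative days are counted for complex cases only;
- the printed model.

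**How it is analysed.** Randomization is in blocks of 4, stratified by surgeon/specialty. Under Randomization & Statistical Analysis, t-tests or Wilcoxon-Mann-Whitney tests "will be used to compare mean orbital volume differences and operative times". Length of stay and costs will probably be compared by t-tests on the log scale. Multivariable models are optional and aimed at complications and departures from normal recovery. The Data Collection table records fracture type and other injuries pre-operatively.

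**The concern.** Fracture type is a plausible strong predictor of operating time, hardware and hospital days. The plan itself treats it so for length of stay, where the counting rule differs between isolated and complex cases. A pre-bent orbital plate does not change which type of fracture a patient has, so between-type variation is noise for the treatment comparison. The plan neither stratifies on this variable nor adjusts for it, yet collects it.

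At stake are secondary outcomes that carry much of the argument for the technique. Operating time is a listed outcome and the main rationale for the cost hypothesis (Hypothesis 4). Length of stay is Hypothesis 3. With about 30 patients per arm, a real but modest saving could be missed, or an uneven split of complex cases could create or hide a difference.

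**Working it through.** **1. The plan's own figure.** The plan gives a "sample size of 60", power to "detect at least a 1 cm³ difference in orbital volume", and "alpha level of .05, and 1.17 cm³ standard deviation of orbital volume". A two-sided two-sample t-test (sidedness is not stated, so two-sided is assumed) with difference 1, SD 1.17 and 30 per arm has power 0.902; 29 per arm gives 0.892. With a 25% shortfall (22.5 per arm) power is 0.800, which agrees with "our study would still retain a power of 80"%. Both figures reproduce, but for orbital volume only. No power is stated for operating time, length of stay or charges.

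**2. Share of complex cases.** The Background gives 90 isolated fractures among 126 in total, so 126 − 90 = 36 complex, and p = 36/126 = 28.6%, or about 17 of 60. These are cases seen at the site, not filtered by the eligibility criteria. The same section cites 66% complex from the literature.

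**3. Other inputs.** The smallest saving quoted under Aim 4 is 0.40 h = 24 min, for laser-melted implants rather than the study technique. The within-type SD s (20 to 30 min) and the extra time D in complex cases are assumptions; the documents give neither.

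**4. Pooled SD and power.** Pooled SD = √(s² + p(1−p)D²), with p(1−p) = 0.204. For example, s = 30 and D = 60 gives √(900 + 735) = 40.4. Power is for 24 min, 30 per arm, two-sided alpha 0.05, by noncentral t.

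| Extra time D | Pooled SD (s = 20; s = 30) | Unadjusted t-test power (s = 20; s = 30) |
|---|---|---|
| 0 min | 20.0; 30.0 | 99.5%; 86% |
| 30 min | 24.2; 32.9 | 97%; 79% |
| 60 min | 33.7; 40.4 | 77%; 62% |
| 120 min | 57.8; 62.0 | 35%; 31% |

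Adjusting for fracture type removes the D term, so power returns to about the first row (99% to 86%) whatever D is. With 66% complex and s = 30, unadjusted power is 79%, 60% and 30% at D = 30, 60 and 120, so the share matters little.

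**5. The planned alternative test.** By simulation, Wilcoxon power is similar to the t-test at D = 60. At D = 120 it is about 68% (s = 20) and about 40% (s = 30): better than the t-test, still well below the adjusted analysis.

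**6. Larger savings.** For a 60-min saving, unadjusted t-test power exceeds 99% at D = 60 and is 96% to 98% at D = 120. At the top of the cited range (3.82 h = 229 min) it is near 100%.

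**7. Chance imbalance.** The SD of the between-arm difference in complex share is √(2 × 0.204/30) = 0.117, or 3.5 patients. One such SD moves the arm difference by 0.117 × 60 = 7 min at D = 60 and by 14 min at D = 120. A gap of 6 or more complex cases has probability of about 11%.

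**8. Bias.** In 20,000 simulated null trials with D = 120 and s = 30, the unadjusted t-test rejected in 5.0%. The problem is noise, not a shifted estimate.

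**9. Charges (dollar scale, for illustration).** One counted hospital day equals 1,690/33 = 51 operating-room minutes. If a complex case carries one extra day and one extra stock implant ($1,690 + $1,364 = $3,054, assumed), this source alone contributes 0.117 × 3,054 ≈ $356 to the standard error of the arm difference. With three extra days ($6,434) it contributes about $750. A 24-min saving is worth 24 × 33 = $792.

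**The case against.** **The stopwatch is already confined to the orbit.** A reader might infer that the clock runs through repair of the rest of the face. In context it does not say so. The preceding bullets use the same words for exposing orbital fractures, and implant means the orbital implant throughout. Work before orbital exposure or after implant fixation is outside the window. Other repairs enter only if done inside it, and no section describes that. This objection stands: what is missing is an explicit statement, including what happens to the clock if other work intervenes.

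**All plates and screws are charged.** This too is tempting to infer. The text leaves the scope of hardware open; it does not set a rule to count everything.

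**Stopwatch minutes are priced at $33.** The documents do not say this either. The charge uses an undefined surgical time within charges that include anesthesia, so a change to the stopwatch might leave charges untouched.

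**The size rests on assumptions.** This is correct. The SD and extra minutes are assumed, 24 min is the least favourable cited saving, and the Wilcoxon option softens the worst case.

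**Balance will be checked first.** The unadjusted tests are conditional on the groups proving balanced, and fracture type could be among the characteristics examined. But no fallback is given if balance fails, and a passed check does not remove between-type variance from the comparison.

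**Conclusion.** The point holds as one of avoidable imprecision. Operating time, length of stay and charges are compared without using a recorded baseline variable that can be expected to predict all three. Randomization protects against systematic bias, and the primary outcome's sample size is unaffected.

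The loss ranges from slight to severe. For a 24-min saving, with s = 20 to 30 min and 29% complex, power falls from about 99% to 86% with adjustment to 97% to 79%, 77% to 62% or 35% to 31% without it, as the extra time in complex cases goes from 30 to 60 to 120 min. It is small if the true saving is 60 min or more. A claim that facial work outside the orbit will swamp these comparisons cannot be supported: the documents supply neither the SD nor the extra time, and the timing window read in context is orbital. The case for adjustment does not depend on those figures, because it costs almost nothing if complex cases turn out to be no different.

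**What to change.** Pre-specify fracture type (isolated versus complex, as recorded pre-operatively) as a term in the operating-time model and in the log-scale models for length of stay and charges, whatever the balance check shows. The cost is one degree of freedom and one sentence in the analysis section. No new data are needed, and the sample size and primary analysis stay as they are.

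As supporting clarifications, at the cost of a line each and a little extra recording:
- state that the stopwatch refers to the orbital repair only, and that any other repair done within the interval is timed separately;
- state that hardware charges refer to the orbital repair only;
- say whether the surgical time priced at $33 per minute is the stopwatch interval or a different one.

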The primary outcome variable is the orbital volume of the injured orbit compared to the contralateral uninjured orbit as assessed by CT scan with OsiriX medical imaging software (OsiriX MD 8.5.2) **at immediate post-operative hour**.

Accordingly, the primary outcome variable will be classified as:

- A. The absolute reduction in orbital volume from the measured post-traumatic volume, as measured by CT.

The secondary outcome variables will be recorded 1 week, 3 weeks, and 6 weeks postoperatively.

The secondary outcome variables include the following:

- 1- Adequate orbital volume reduction, defined as a reduction of orbital volume to **less than 2 cm³**.
- 2- Unsatisfactory orbital volume, defined as a final orbital volume **more than 2 cm³**
- 3- Post-operative variables: enophthalmos, infection, infraorbital nerve injury, traumatic pupillary mydriasis, orbital compartment syndrome, extra-ocular motility, and plate contour.
- 4- Operating time.
- 5- Length of stay (LOS).
- 6- Treatment charges.

The following are details regarding secondary outcome variables:

- Enophthalmos as assessed by clinical examination using a Hertel exophthalmometer.
 - A difference of more than 2 mm between the two orbits is diagnostic for enophthalmos.⁽⁴⁾
- Infection
 - As defined by the presence of post-operative pus in the wound, a sinus tract or fistula, or elevated WBC >11.0x10⁹/L combined with erythematous skin and swelling on the operated side more than on the un-operated side.
- Infraorbital nerve injury as assessed by clinical examination using neurosensory testing (NST).
 - i. NST is a standardized methodology designed to objectively evaluate sensory nerve function.⁽²²⁾ The sensory impairment is determined by 3 levels of testing; each level classifies a specific type of sensory nerve injury.^(22, 23)
 - ii. All patients will be assessed for the development of altered sensation of the infra-orbital nerve that:
 - A. Did not present prior to the surgery.
 - B. Did not improve after the surgery.
- Traumatic pupillary mydriases as assessed by pupillary size measurement in millimeters.
 - All patients will be assessed for the development of post-operative traumatic pupillary mydriasis that did not present prior to the surgery.
- Orbital compartment syndrome as assessed through clinical examination using tonometers.
 - Intra-ocular pressure (IOP) > 40 mmHg is diagnostic of orbital compartment syndrome.

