Data	Time
Age, sex, race, DOB	Pre-operative (pre-op)
Mechanism of injury, time from injury to admission	Pre-op
Type of orbital fracture and other injuries	Pre-op
Indications for surgery	Pre-op
CT scans results (fracture size & location)	Pre-op
Extra-ocular motility indicating which gaze	Pre-op
Level of infraorbital nerve injury	Pre-op
Traumatic pupillary mydriasis	Pre-op
IOP (Intra-ocular pressure)	Pre-op
Enophthalmos (Hertel exophthalmometer measurement)	Pre-op
The use of 3D printed models	Pre-op
The time needed to print the model	Pre-op
Orbital and ocular exam results	Pre-op
Time from admission to surgery	Pre-op
Date of surgery	Pre-op
Length of surgery (minutes)	Operative
Approach	Operative
Intra-operative complications	Operative
Post-operative orbital volume comparison (OsiriX)	Post-operative
Dates of post-operative visits	Post-operative, weeks 1, 3, and 6
Extra-ocular motility indicating which gaze	Post-operative, weeks 1, 3, and 6
Level of infraorbital nerve injury	Post-operative, weeks 1, 3, and 6
Traumatic pupillary mydriasis	Post-operative, weeks 1, 3, and 6
IOP (Intra-ocular pressure)	Post-operative, weeks 1, 3, and 6
Infection	Post-operative, weeks 1, 3, and 6
Enophthalmos (Hertel exophthalmometer measurement)	Weeks 1, 3, and, 6

Overall cost	Post-operative
Need for second surgical procedure	Post-operative, weeks 1, 3, and 6

SIGNIFICANCE AND INNOVATION

This project will test two new and evolving methodologies in the medical world: 1) an office-based 3D printer and 2) pre-adjusted patient-specific implants. These two methodologies have yet to be applied together in orbital fracture reconstruction. Additionally, this study focuses on low-income patients and will be the first of its kind serving this population. Several other benefits include potential savings related to total overall cost, a reduced operative time and postoperative course, and a subsequent increase in both the quality of care and the value of care, especially in the underserved patient population cared for at GMH. We expect the results of this study to be applicable at most major urban trauma centers across the USA and abroad. The results of this study can be used in future studies as a model or pilot study.

FUTURE PLANS

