3. All subjects will sign consent and HIPAA forms.
4. All data will be collected by the residents within oral and maxillofacial surgery, the ENT or plastics training program, or by the PI or co-PIs.
5. All consent, HIPAA, and data collection forms will be stored in a locked office. Data will be entered into a research-designated laptop within the same office, which is password-protected.
6. Patient confidentiality will be maintained in part because no forms or documentation pertaining to study participation are included in the patient's medical record.
7. All data will be scrubbed to remove identifiers after study completion.
8. Patient monitoring will be performed by the PI and the Research Assistant.
9. All adverse events (AEs) will be graded as to their attribution (unrelated to protocol, or possibly, probably, or definitely related to protocol). AEs will be reported to either the PI, co-PI, research assistant, or residents by a study subject or by medical staff caring for the subject. No adverse events are expected in this pilot study. Observed as well as serious AEs will be recorded and reported per IRB and ROC standard protocols. Serious AEs are predefined as any experience that suggests a significant hazard, such as events that: a) are fatal, b) are life-threatening, c) result in permanent disability, d) require inpatient hospitalization or e) involve cancer, a congenital anomaly, or drug overdose.

BIBLIOGRAPHY

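### The PI reads the primary outcome, and nothing in the plan masks that reading or keeps arm data from the PI until the volumes are fixed

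*Combined protocol and SAP*

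**What the plan says.** All references are to the combined protocol and SAP.

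- **Outcome.** Under Study Settings and Patients, the primary outcome compares the injured with the uninjured orbit on CT at the immediate post-operative hour. It is then specified as "The absolute reduction in orbital volume from the measured post-traumatic volume, as measured by CT".
- **Reader.** Postoperative Assessment, item 2: "The PI will evaluate the orbital volume using OsiriX". No second reader is named and no coding of scans is described.
- **Masking.** Randomization & Statistical Analysis leaves physician and patient unblinded and has the allocation envelope opened at enrollment, so the arm is disclosed before the post-operative CT exists. The only blinding in the document is that of the ophthalmology team, under Preoperative Assessment.
- **The PI's other roles.** Follow-Up, on who handles the data ("In terms of data collection and data extraction from Epic"), lists the PI and a co-PI and adds that "an assigned research coordinator will be involved". Human Subject Protections, item 4, says that all data are collected by residents in oral and maxillofacial surgery, "the ENT or plastics training program, or by the PI or co-PIs". Item 8: "Patient monitoring will be performed by the PI and the Research Assistant".
- **An item that reveals the arm.** The Data Collection & Analysis table includes "The use of 3D printed models", recorded pre-operatively.
- **Related readings.** Plate contour is judged on the same CT, with no reader named. Follow-Up has the surgical team record enophthalmos at weeks 1, 3 and 6.

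**The concern.** The primary comparison rests on a measurement by one person whose other duties bring them close to the allocation. If placing the orbital boundary involves any judgement, a reader who knows the arm can favour the new method without intending to. Such a shift goes straight into the between-arm difference, and a larger sample does not remove it. The plan calls concealment of the procedure impractical, but that reason applies to surgeon and patient. It does not apply to someone reading stored scans. Since the ophthalmology team is blinded, masked assessment was evidently thought feasible, yet it was not extended to the primary outcome.

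**Working it through.** **1. Can the PI learn the arm before reading?** The relevant statements, side by side:

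| Statement | Effect on the CT reading |
|---|---|
| Arm revealed at enrollment | Known to the team before the post-operative CT |
| PI takes part in data collection and Epic extraction | Opens a route to arm data |
| Use of a 3D printed model is a collected item | Reveals the arm |
| PI monitors patients | Opens a second route |
| Ophthalmology team blinded | Covers the ocular examination; the ophthalmology attending is a Co-PI, listed separately from the PI who reads volumes |
| Measures to limit bias in printing and plate bending | Concern the intervention, not the outcome reading |
| In the medical record, "no forms or documentation pertaining to study participation are included" | Limits what Epic shows, but does not cover the study's own data forms |

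No statement closes the routes in rows 2 to 4.

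**2. The plan's own sample size.** Inputs from Randomization Sample Size & Calculation: difference 1 cm³, SD 1.17 cm³, alpha 0.05 (taken as two-sided), power 90%.

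- SE = 1.17 × √(2/30) = 0.302 cm³; noncentrality = 1/0.302 = 3.31; df = 58.
- Required n = 29.76, so 30 per arm and 60 in total. Power at 30 per arm is 90.2%.

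The stated 60 reproduces. Masking the reading does not change it.

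**3. What a reading shift would do (illustration).** Assume no true difference and a constant shift b in favour of the new plate. The noncentrality is b/SE, and the chance of a significant result favouring the new plate is P(T > 2.002), where T is noncentral t with 58 df. At b = 0 this is 2.5%.

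The plan describes 1.17 cm³ as the SD of orbital volume, so the SD of the compared difference is an assumption. Taking the injured-minus-uninjured difference, it is 1.17 × √(2(1−r)), with r the assumed correlation between the two orbits: 1.65 at r = 0, 1.17 at r = 0.5, 0.80 at r = 0.77.

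| Assumed SD (cm³) | SE | b = 0.1 | b = 0.2 | b = 0.3 |
|---|---|---|---|---|
| 0.80 | 0.207 | 6.9% | 15.7% | 29.7% |
| 1.17 | 0.302 | 5.1% | 9.5% | 16.3% |
| 1.65 | 0.426 | 4.2% | 6.7% | 10.3% |

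If masking only halved the shift, the SD 1.17 row would become 3.6%, 5.1% and 7.1%.

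**4. Minor: the stated imbalance bound.** With two allocations to each arm in a block of 4, the running difference is 1 after the first case, 0 or 2 after the second, 1 after the third and 0 after the fourth. The maximum is 2 per list, not 3. The plan's total of 9 implies 9/3 = 3 lists, which fits the three specialties named for plate bending. The overall maximum is then 3 × 2 = 6, so 9 cannot occur. This has no material effect on power: even a 27 v 33 split gives 89.9%.

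**The case against.** The strongest counter-argument is that the harm is not shown. No statement says that the PI knows any patient's arm. The protocol describes OsiriX as precise and does not say whether the segmentation is manual or automatic, so the role of reader judgement is an assumption. The shifts and SDs are also assumed. The SD range describes a between-orbit difference, whereas the outcome is also specified as a reduction from the post-traumatic volume, whose SD is not given. All of this stands, and it is why the figures are only an illustration. Precision, however, does not protect against a reader's expectation, and no operator-independent method is specified.

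A second objection is that coded scans cannot hide a plate visible on CT, and that a PI who has monitored a patient may recognise the case. This also stands. Masking may be partial, and coding alone is not enough for patients whom the PI knows.

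A reader might infer that the PI is unblinded, or that the primary result will be biased. The documents support neither. Staff names are removed, so it cannot be told whether the PI operates or prints models. A reader might also take the per-list bound of 3 as false. It is only loose, because 2 is within it. Nor do arm sizes require complete blocks to be equal: a list that stops two cases into a block is balanced in 4 of 6 orders.

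**Conclusion.** The concern holds as a missing safeguard on the primary outcome. The PI reads the volumes, nothing masks that reading, and nothing keeps arm data from the PI until the volumes are fixed. That the PI could know the arm is an inference from the roles described, not a stated fact. At an assumed SD of 1.17 cm³, an assumed shift of 0.2 cm³ would roughly quadruple the chance of a false result favouring the new plate (2.5% to 9.5%), but the documents give no basis for choosing that shift over a smaller one or none. The amendment should be made because it is inexpensive and protects the main comparison. It does not call the sample size into question.

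The enophthalmos point is secondary. The unblinded surgical team records it, while the blinded ophthalmology team also examines patients after surgery, and the plan does not say whose reading is used. The imbalance bound is a minor wording matter.

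**What to change.** 1. **Mask the CT reading.** Amend Postoperative Assessment, item 2, so that the assigned research coordinator codes the pre- and post-operative CTs, removes identifiers and arm, and supplies them in random order. Lock the volumes and the plate-contour rating before the reader sees the 3D-model items or other arm data. Complete the coding before study data are stripped of identifiers at the end of the study.
2. **Separate the duties.** Until the lock, have the coordinator, or a co-PI outside the blinded ophthalmology team, handle the data items that reveal the arm. Where the PI has operated on, printed for or monitored a patient, a member of the existing study team without that contact should read that patient's scans where possible.
3. **Report residual unmasking.** If an arm guess is collected, record it only after the volume is locked, so that it does not draw attention to the arm before measurement. Report it descriptively, since a true difference in fit could also make guesses correct.
4. **Enophthalmos.** Where the blinded ophthalmology team takes a post-operative Hertel reading, use it in preference to the surgical team's. The documents do not place that team at weeks 1, 3 or 6, so the plan should state when such readings exist.
5. **Minor wording.** State the bound as 2 per list (6 if there are three lists), and say that equality at completion is guaranteed only when every list ends on a complete block.

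**Cost.** Coordinator time for about 60 × 2 = 120 scans, a short amendment, and some data duties moved from the PI until the lock. The CTs are already standard of care, so no scans or visits are added and the sample size is unchanged. Because the plate is visible on CT, masking may be incomplete.
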